8.3.2.3. Sensitivity Analysis

Due to changes in clinical practise, we will evaluate our original model on patients treated and not treated with Clonidine.

8.3.2.4. Supplementary Analysis

Not relevant

8.3.3. Secondary Endpoint Analysis

Only main outcome, postdischarge pain will be analysed.

8.3.4. Tertiary/Exploratory/Other Endpoint(s)/Estimand(s) Analysis

Not relevant

8.3.5. Other Safety Analyses

Not relevant

8.3.6. Other Analyses

Not relevant

Interim Analysis

Will not be performed. All data will be collected in estimated 6 months and data analysis will be performed shortly after all patients are included.

8.5. Sample Size Determination

The logistic regression model which will be validated includes 4 variables and one additional variable to adjust for the possible confounding effect of being treated with Clonidine, thus will require at least 75 patients who report severe post-discharge pain. Based on our

previous research, we anticipate that 40% will report severe postdischarge pain, therefore we aim to include at least 188 patients. Allowing for 10% drop-outs/loss to follow up we aim to include 207 patients. We anticipate including approximately 40 patients monthly, thus we will be able to include 207 patients in 5 to 6 months. This sample size will enable us to perform all pre-planned analyses with sufficient statistical power and provide estimates with sufficient precision.

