1.1. Synopsis

Protocol Title: Validation of a risk matrix for severe postdischarge pain after ambulatory gynaecological laparoscopy

Brief Title: Predicting pain after ambulatory gynaecological laparoscopies

Rationale:

Objectives, Endpoints, Assessments:

Objectives	Endpoints	Assessments
Primary		

 To validate a prediction tool for severe postdischarge pain (NRS 7-10) after gynaecological laparoscopic surgeries 	
 Worst pain since discharge from hospital within 24 h after surgery 	
 Pain assessment using the Verbal Numeric Rating Scale 0-10, on POD1

Study design: Prospective observational cohort study

This study design includes no masking.

Brief Summary:

The purpose of this study is to test and validate a newly developed risk matrix in a new sample of patients. The risk matrix will be a useful tool to preoperatively predict who is at risk for experiencing severe postoperative pain after discharge from ambulatory gynaecological surgery. When validated, the prediction tool will be implemented in everyday clinical practice with ambulatory gynaecological patients.

Study details include:

- The study duration will be up to 6-7 months.
- Data will be collected at three occasions, on the day of surgery, during PACU stay and on POD1.

Number of Participants:

Approximately 207 participants (minimum) will be enrolled in the study.

Schema

Procedure	Day of surgery	PACU	POD1	Notes
Written informed consent	x			
Inclusion/exclusion criteria	x			
Demography/Baseline data	x			Questionnaire
Postoperative pain		x		
Postdischarge pain			x	Postdischarge pain data collected by telephone follow-up
Intraoperative data collection			x	Patients' medical records (Dips and MetaVision)

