8.3. Statistical Analyses

8.3.1. General Considerations

We will compare the collected sample with the previously collected sample on selected baseline variables to assess possible selection bias and generalisability of our results. Due to changes in clinical practise, a majority of patients is now treated with Clonidine, which was not the case when the matrix was developed. To avoid unnecessary delays in recruiting and to ensure that the results will be relevant for todays' patients, we will include patients treated with Clonidine. The previously developed risk matrix will be applied on the data and the predicted and observed outcomes will be compared. In case of under- or over-estimation, the risk matrix will be calibrated.

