8.3.2.2. Main Analytical Approach

We will validate the performance of a newly developed risk matrix. We will compare the predicted probabilities of worse postdischarge pain using the risk model with the recorded values. Further, we will perform comprehensive validation. The observed and predicted outcomes will be arranged in a confusion matrix. Further, we will investigate discrimination ability of the model by computing AUC (area under the curve) and c-statistics. Overfitting will be assessed by computing a calibration slope. Finally, we will refit the prediction model and perform tuning of the model parameters. Due to changes in clinical practise, we will include both patients treated and not treated with Clonidine. To investigate the effect of being treated with Clonidine, we will include this variable as a possible confounder.

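### Section 8.5 sizes a five-term refit rather than the validation of the four-factor matrix, and the planned refit has no optimism correction

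*Combined protocol and SAP*

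**What the plan says.** Sections 3, 8.1 and 8.3.1 make a previously developed risk matrix the object of validation. Section 2.2 names four preoperative factors behind it: age, preoperative pain, pain expectation and preoperative opioid use. Section 8.3.1 adds that most patients now receive Clonidine, unlike when the matrix was developed, and states: "The previously developed risk matrix will be applied on the data and the predicted and observed outcomes will be compared".

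Section 8.5 describes the model differently: "The logistic regression model which will be validated includes 4 variables and one additional variable to adjust for the possible confounding effect of" Clonidine treatment. It asks for 75 events on that basis, expects 40% with severe pain, and arrives at 188 patients, or 207 with 10% for losses. It concludes: "This sample size will enable us to perform all pre-planned analyses with sufficient statistical power and provide estimates with sufficient precision".

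Section 8.3.2.2 opens with the risk matrix and a comparison of its predictions with the recorded outcomes. It continues:

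- "Further, we will investigate discrimination ability of the model by computing AUC"
- "Overfitting will be assessed by computing a calibration slope"
- "Finally, we will refit the prediction model and perform tuning of the model parameters"
- "To investigate the effect of being treated with Clonidine, we will include this variable as a possible confounder"

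No bootstrap, cross-validation or shrinkage is mentioned for the refit. The synopsis says what follows from success: "When validated, the prediction tool will be implemented in everyday clinical practice with ambulatory gynaecological patients".

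**The concern.** A matrix that already exists has nothing left to estimate. Validating it means applying it unchanged and measuring discrimination and calibration, so the sample size question is how precisely those measures will be known. A count of events per model term answers another question: how many patients are needed to fit a model. Section 8.5 uses the second kind of reasoning, attaches it to a five-term model that it calls the one to be validated, and then claims adequate precision without giving an interval width for any validation measure.

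The planned refit and tuning raise a related matter. Performance measured on the patients used for fitting is flattering, and nothing in the plan corrects for that. Since the tool is to enter routine care once validated, readers need to know how firm the evidence for the unchanged matrix will be, and must be able to tell it from figures for an updated model.

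**Working it through.** **1. The plan's own figures.** Section 8.5 gives 75 events, 40%, 188, 10% and 207. The rule behind 75 is not written down. With five terms it is 75/5 = 15 events per term.

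- 15 × 5 = 75 events
- 75/0.40 = 187.5, so 188
- 188 × 1.10 = 206.8, so 207

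The figures reproduce. The same rule with four terms gives 60 events, 60/0.40 = 150, and 150 × 1.10 = 165. That is the previous sample size in the amendment table, used here only to support the inferred rule. The extra 207 − 165 = 42 patients come from counting Clonidine as a fifth term.

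**2. Which model this sizes.** The matrix rests on four factors and no Clonidine coefficient for it is described. A model with a Clonidine term must therefore be estimated on the validation patients, which is model updating. Section 8.5 can also be read as a four-variable model plus an adjustment term, but the count uses five terms either way.

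**3. Precision for the unchanged matrix at N = 188.** Inputs: 75 events and 113 non-events (from 8.5); AUC of 0.65, 0.70 or 0.75 (assumed).

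For the AUC (A), Hanley–McNeil: SE² = [A(1−A) + (n₁−1)(Q₁−A²) + (n₀−1)(Q₂−A²)]/(n₁n₀), with Q₁ = A/(2−A) and Q₂ = 2A²/(1+A).

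Example at A = 0.70: Q₁ = 0.5385 and Q₂ = 0.5765. Then SE² = [0.21 + 74 × 0.0485 + 112 × 0.0865]/8475 = 0.00159, so SE = 0.0399 and 1.96 × SE = 0.078.

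For the calibration slope: Fisher information for a logistic regression of outcome on the matrix's linear predictor L. The true slope is 1, and L is assumed normal within outcome groups. With w = p(1−p), SE² = mean(w)/{n[mean(w)·mean(wL²) − mean(wL)²]}.

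| Assumed AUC | AUC SE | AUC 95% half-width | Slope SE | Slope 95% half-width | Expected slope interval |
|---|---|---|---|---|---|
| 0.65 | 0.0415 | 0.081 | 0.292 | 0.57 | 0.43 to 1.57 |
| 0.70 | 0.0399 | 0.078 | 0.226 | 0.44 | 0.56 to 1.44 |
| 0.75 | 0.0376 | 0.074 | 0.189 | 0.37 | 0.63 to 1.37 |

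At the earlier 150 analysed patients the AUC half-widths would be 0.091, 0.088 and 0.082, so the added patients also help the validation a little.

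**4. Optimism of the refit.** The documents give no coefficients, so every input here is assumed: an unpenalised five-term logistic refit on 188 patients with mean risk 0.40 and underlying AUC of about 0.65 to 0.75.

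| Set-up | Own-data AUC minus AUC in new patients | Slope in new patients |
|---|---|---|
| Two continuous and two binary predictors; Clonidine in 55% to 90%, odds ratio 1.0 or 0.6 | 0.019 to 0.045 | mean 0.75 to 0.91 |
| Four equal normal predictors; Clonidine in 70%, no effect | 0.028 to 0.046 | median 0.70 to 0.83 |

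The own-data slope of an unpenalised refit is 1 by construction. A ridge refit in the first set-up gave own-data slopes of 1.27 to 1.34, which is no more a validation result. In a check of the remedy, a bootstrap estimated the AUC optimism at 0.023 to 0.039 against an actual 0.023 to 0.044.

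**The case against.** The strongest reply is that the existing matrix plainly is tested first. Section 8.3.1 applies the previous matrix to the new data. Section 8.3.2.2 opens with that matrix, so the model in its AUC sentence most naturally means the same one, and the refit comes last. Section 8.3.2.3 again evaluates the original model. This stands. Naming the matrix beside the AUC and slope is a clarification, not the repair of an error.

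A reader might infer that refit performance will be presented as the validation, or that a Clonidine model will be put forward as the tool. The documents do not support either. No section says so, and the tool is meant for use before surgery while Clonidine is given during it. A reader might also infer that 207 patients are too few. That does not follow: the plan sets no precision target, so precision is unstated rather than shown to be inadequate. Sizing for a planned refit is legitimate in itself.

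It is also fair that the opening of section 8 calls itself a summary and defers technical detail to a statistical analysis plan. Optimism correction could be specified there, but the supplied text contains no such detail, and a later plan would not correct what 8.5 says. Finally, the optimism figures depend on the simulation set-up, and a coarse categorical matrix could behave differently from the scores assumed.

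**Conclusion.** The point holds in two parts.

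First, 8.5 gives the wrong label to the model it sizes. The 75 events fit five terms at an inferred 15 per term and do not support the claim of precision for the validation measures. Under normal linear predictors and the assumed AUCs, the calibration slope is the weaker measure: even a perfectly calibrated matrix would have an interval of about 1 ± 0.37 to 1 ± 0.57.

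Second, the planned refit and tuning have no optimism correction. The size is about 0.02 to 0.046 in AUC and an average slope in new patients of roughly 0.70 to 0.91. These are ranges over assumed set-ups, not bounds.

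The arithmetic of 75, 188 and 207 is correct and the data remain usable. This should be settled before analysis.

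**What to change.** 1. In 8.5, stop describing the five-term model as the one under validation and say that the 75 events size the refit. Replace the general precision claim with the expected confidence interval widths for the existing matrix's AUC and calibration slope at N = 188, under stated assumptions. N stays as it is.
2. In 8.3.2.2, classify recalibration, refit, tuning and the Clonidine term as secondary model updating. Correct any reported refit performance for optimism with a bootstrap that repeats the tuning in each resample.
3. As a clarification, name the unchanged four-factor matrix beside the confusion matrix, AUC and calibration slope.

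The cost is rewording in two sections, a short precision calculation and one bootstrap, with no new patients or data. The downside is a little extra analysis and less favourable stated precision and refit performance.

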2.2. Background

Despite the gynaecological laparoscopic procedure being considered less invasive compared to laparotomy (Brown 2019), 20-40% of patients report severe pain postoperatively (Gerbershagen 2013, Cruz 2021), which can negatively impact quality of life, recovery, patient satisfaction, and healthcare resource utilisation. Most of these women undergo ambulatory surgery, meaning they arrive for the operation and return home the same day. Since they have limited access to stronger pain medication upon returning home and lack direct access to medical expertise, unlike inpatients, severe postoperative pain can be both uncomfortable and problematic.

In our previous study, we found that over 42% of the patients experienced severe postdischarge pain within the first 24 h after surgery, that is a pain score of 7-10 on the NRS. We identified 4 preoperative risk factors independently associated with severe postdischarge pain: younger age, presence of preoperative pain, pain expectation and preoperative use of opioids. Our findings may contribute to clinicians’ awareness of clinically relevant risk factors for severe postoperative pain in this patient population. Moreover, knowledge

on females-specific validated predictive factors for pain is important for successful treatment in gynaecological laparoscopic surgery which is one of the most common ambulatory surgical procedures (Joo, 2019).

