8.6.7. Study and Site Start and Closure

First Act of Recruitment

Anticipated start date of the study is November 2025.

Study/Site Termination

According to the sample size calculation (n=188) + at least 10%, we will include at least 207 patients.

Study sites will be closed upon study completion. A study site is considered closed when all required documents and study supplies have been collected and a study-site closure visit has been performed.

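### Minor: the 10% loss allowance is added to 188 rather than divided out, so 207 women included fall just short of 188 evaluable and 75 events, while the end-of-study definition uses 207 in a different sense

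*Combined protocol and SAP*

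**What the plan says.** Section 8.5 (Sample Size Determination) builds the target in three steps.

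- **Events.** The model "includes 4 variables and one additional variable to adjust for the possible confounding effect of being treated with Clonidine", and "thus will require at least 75 patients who report severe post-discharge pain".
- **Women before loss.** From earlier research "we anticipate that 40% will report severe postdischarge pain", and "therefore we aim to include at least 188 patients".
- **Women to include.** "Allowing for 10% drop-outs/loss to follow up we aim to include 207 patients".

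Section 8.6.7 (Study and Site Start and Closure) shows how the last step was done: "According to the sample size calculation (n=188) + at least 10%, we will include at least 207 patients". The synopsis (1.1) also counts 207 at entry: "Approximately 207 participants (minimum) will be enrolled in the study".

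The end-of-study definition in Section 4 uses the same number differently. There the study ends once at least 207 patients have a complete data set, and a participant counts as complete only after answering all questions, including the call on postoperative day 1.

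**The concern.** A loss rate is a fraction of those who enter. To keep 188 after losing 10%, the entry number is 188 divided by 0.90. Adding 10% of 188 gives a slightly smaller number, so a study that includes 207 and loses 10% ends below the 188 and the 75 that the same paragraph sets as minimums.

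The end-of-study definition decides whether this shortfall occurs at all. Read as complete data sets, 207 is more than enough for 75 expected events, but the inclusion target and the loss allowance in 8.5 then describe a different study. What is at stake is a correctly stated sample size with one meaning throughout the protocol. The feasibility of the validation is not in question.

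**Working it through.** **Inputs.** Required events 75, event proportion 40%, women before loss 188, loss 10%, recruitment about 40 a month (all Section 8.5); at least 207 complete data sets (end-of-study definition, Section 4); over 42% severe pain in the previous study (Section 2.2).

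**Reproducing the plan's figure**

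- Events to women: 75/0.40 = 187.5, rounded up to 188.
- Allowance by addition: 188 x 1.10 = 206.8, rounded up to 207. This matches 8.5, and 8.6.7 describes the same addition.

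**Allowance by division**

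- 188/(1 - 0.10) = 208.9, rounded up to 209.
- Check: 209 x 0.90 = 188.1 evaluable; 188.1 x 0.40 = 75.2 expected events.

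**Reading A: 207 women included (1.1, 8.5, 8.6.7)**

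- Evaluable: 207 x 0.90 = 186.3, which is 188 - 186.3 = 1.7 short.
- Expected events: 186.3 x 0.40 = 74.5, which is 0.5 short of 75.
- The shortfall against 188 disappears if loss is at most 1 - 188/207 = 9.2%.
- The shortfall against 75 disappears if the event rate is at least 75/186.3 = 40.3%. At 42% the expected count is 186.3 x 0.42 = 78.2.

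**Reading B: 207 complete data sets (end-of-study definition)**

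- Expected events: 207 x 0.40 = 82.8.
- Women to include at 10% loss: 207/0.90 = 230.
- Recruitment time: 230/40 = 5.75 months, against 207/40 = 5.2 months for 207 included.

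**Chance of reaching 75 events** (binomial; the probability per included woman is 0.90 x 0.40 = 0.36)

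| Design | P(at least 75 events) |
|---|---|
| 207 included, 10% lost | 0.50 (5th to 95th percentile 63 to 86 events) |
| 209 included, 10% lost | 0.54 |
| 188 evaluable | 0.54 |
| 207 complete | 0.88 |

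Correcting the division moves the probability only from 0.50 to 0.54.

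**The case against.** The strongest reply is that the shortfall depends on one reading of 207. Under the end-of-study definition, recruitment continues until 207 data sets are complete, and 82.8 events are expected. Section 5.3 leans the same way, since it gives loss to follow-up and lost recordings as examples of screen failure. This stands: the documents do not support an unconditional claim that the design misses its own minimum. It does not rescue 8.5, however. There 207 is the number to include with the 10% loss still to come, and the synopsis and 8.6.7 also count women at entry.

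Second, 207 is called a minimum in 1.1 and 8.6.7, so two more women already fit the text. That is true, although a floor of 207 also permits stopping at 207.

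Third, the gap is negligible: about 1% of the sample and half an event, removed by a loss of 9.2% or an event rate of 40.3%. Section 2.2 reports that "we found that over 42% of the patients experienced severe postdischarge pain within the first 24 h after surgery", so 40% is already on the low side. This also stands, and it is why the point is minor.

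A reader might infer that the dropout slip is what makes the event minimum fail about half the time. The figures do not support that. A near-even chance arises whenever a study is sized so that the expected count equals the requirement, and it remains with 209 included. It can fairly be said that 8.5 states what the model needs and promises no yield; even so, on the included reading a clarifying phrase is worthwhile, because the calculation makes 75 an expectation only.

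**Conclusion.** The point holds as a minor correction. Section 8.5 adds the allowance where it should divide, giving 207 where its own inputs give 209. If 207 means women included, and loss is exactly 10% and the event rate exactly 40%, about 186 evaluable women and 74.5 events are expected, some 2 women and 0.5 event under the stated 188 and 75. If 207 means complete data sets, there is no shortfall, but the inclusion target is understated by about 230 - 207 = 23 women.

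The documents do not settle which meaning governs. Three places count women at entry and one counts complete data sets. That inconsistency matters more than the rounding-sized gap, and correcting 8.5 alone would leave it in place. It would be wrong to conclude that the study is materially undersized because of this slip.

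**What to change.** State in 8.5 which meaning of 207 governs, and make 1.1, the end-of-study definition in Section 4, 8.5 and 8.6.7 agree.

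- **If 207 means women included:** either change it to 209, or keep 207 and restate its yield as about 186 evaluable women and an expected 74 to 75 events (90% range 63 to 86). Align the end-of-study definition to the evaluable number. Say that 75 is the expected event count and not a guaranteed minimum, since the chance of at least 75 is about 0.5 with either 207 or 209 included.
- **If 207 means complete data sets:** restate the inclusion target as about 230 at 10% loss, with recruitment of about 5.75 months at 40 a month.

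The cost is a wording change in four places. The first option adds at most two women (2/40 = 0.05 month). The second adds about 23 women to the stated inclusion target and about 23/40 = 0.6 month, still within the 5 to 6 months that 8.5 anticipates.

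### Section 8.5 sizes the study for a five-term refit only, yet claims sufficient power and precision for every planned analysis; 207 is also used both as the number included and as the number complete

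*Combined protocol and SAP*

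**What the plan says.** Section 8.5 counts five model terms (four predictors plus Clonidine) and sets a requirement of 75 patients with severe pain. It continues: "we anticipate that 40% will report severe postdischarge pain, therefore we aim to include at least 188 patients". Then: "Allowing for 10% drop-outs/loss to follow up we aim to include 207 patients". It closes with the adequacy statement: "This sample size will enable us to perform all pre-planned analyses with sufficient statistical power and provide estimates with sufficient precision".

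The analyses that this statement covers are set out elsewhere:

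- Section 8.3.2.2 plans a confusion matrix and a refit with tuning, with Clonidine added as a possible confounder. On discrimination, "we will investigate discrimination ability of the model by computing AUC (area under the curve) and c-statistics". On calibration, "Overfitting will be assessed by computing a calibration slope".
- Section 8.3.2.3 adds that "we will evaluate our original model on patients treated and not treated with Clonidine".
- Section 8.3.1 says that "a majority of patients is now treated with Clonidine, which was not the case when the matrix was developed", and attaches an action to the comparison of predicted with observed outcomes: "In case of under- or over-estimation, the risk matrix will be calibrated".

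The number 207 appears in two senses. In the Synopsis, Section 8.5 and Section 8.6.7 it is the number enrolled or included; in 8.5 and 8.6.7 the 10% loss is already built in. In the End-of-Study Definition (Section 4) it is the number of patients with complete data.

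**The concern.** A count of events per model term is a rule for fitting a model. The main purpose here is to validate an existing one, and what matters for that is how tightly the event rate, AUC and calibration slope will be estimated. Section 8.5 gives no alpha, power, expected AUC, target interval width or Clonidine share, so nothing in it supports a claim of sufficiency for those measures. The claim is weakest for patients not given Clonidine, who by the plan's own account are a minority.

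The results have consequences. The matrix is to be recalibrated if it over- or under-predicts, and the Synopsis says it will go into routine use once validated. A reader of 8.5 would take the estimates behind those steps to be precise. The double use of 207 adds to this, because it decides whether the event requirement is comfortably met or roughly a coin toss.

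**Working it through.** **1. The plan's own figure.** 75 events / 5 terms = 15 per term (implied, not stated). 75 / 0.40 = 187.5, so 188. 188 x 1.10 = 206.8, so 207. The chain reproduces. The previous size of 165 in the amendment table follows the same rule: 4 x 15 / 0.40 = 150, and 150 x 1.10 = 165.

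**2. What 207 yields.** Multiplying by 1.10 does not quite offset a 10% loss; 188 / 0.9 = 208.9, so 209 included would be needed to keep 188. The two senses of 207 give:

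| Reading | Included | Analysed | Expected events at 40% | P(at least 75 events) |
|---|---|---|---|---|
| 207 included, 10% lost | 207 | 207 x 0.9 = 186 | 74.4 | 0.49 |
| 8.5 as stated | 207 | 188 | 75.2 | 0.54 |
| 207 complete | 207 / 0.9 = 230 | 207 | 82.8 | 0.88 |

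The probabilities are exact binomial. At 42%, the earlier cohort's rate in Section 2.2 (given there as just over 42%), they are 0.70, 0.74 and 0.96. At 35% (my assumption; no Clonidine effect size is given) they are 0.08, 0.09 and 0.38. They bear on the refit, not on the AUC or slope.

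**3. Event rate.** This is the measure closest to the recalibration trigger and needs no AUC assumption. Half-width = 1.96 x sqrt(0.4 x 0.6 / n). For n = 186 it is 7.0 percentage points; for n = 207 it is 6.7.

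**4. AUC and calibration slope.** The documents give no AUC, so I assumed 0.65, 0.70, 0.75 and 0.80. The AUC standard error is from the Hanley-McNeil formula. The slope standard error is from the inverse Fisher information of a logistic recalibration model (intercept and slope), with true slope 1, 40% events and a normal linear predictor whose mean and SD are solved to give each AUC. 95% half-widths:

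| Sample | Measure | AUC 0.65 | 0.70 | 0.75 | 0.80 |
|---|---|---|---|---|---|
| Pooled, 186 | AUC | 0.08 | 0.08 | 0.07 | 0.07 |
| Pooled, 186 | slope | 0.58 | 0.45 | 0.37 | 0.33 |
| Pooled, 207 | slope | 0.55 | 0.42 | 0.35 | 0.31 |
| Untreated at its 50% bound, 93 | slope | 0.81 | 0.63 | 0.53 | 0.46 |
| Untreated at an assumed 30%, 56 | slope | 1.05 | 0.81 | 0.68 | 0.60 |

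So a perfectly calibrated matrix would have a pooled slope interval of about 0.42 to 1.58 at AUC 0.65, or 0.67 to 1.33 at AUC 0.80.

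**5. Untreated stratum.** A treated majority means fewer than 186 / 2 = 93 untreated patients, hence fewer than about 93 x 0.40 = 37 events (about 41 with 207 analysed), if the 40% rate applies there. At the 50% bound the event-rate half-width is 10.0 points.

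**6. Limits of the slope figures.** They are asymptotic and treat the predictor as continuous and normal, whereas the tool is a matrix whose cells the documents do not give. They are optimistic in small samples: simulation (2,000 runs per setting) at AUC 0.80 gives 0.33 for 186 patients, as above, but 0.50 for 93 and 0.71 for 56.

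**The case against.** The strongest reply has five parts.

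- **The event count is relevant.** Section 8.3.2.2 does plan a refit with five terms, and 75 events speaks directly to that. This stands, which is why the adequacy sentence should be narrowed to the refit and not simply deleted.
- **The slope is the wrong measure for the recalibration decision.** Section 8.3.1 acts on over- or under-estimation, while Section 8.3.2.2 assigns the slope to overfitting. This also stands. The event rate, at about 7 points pooled, is the nearer measure, and the slope widths should not be read as the precision of that trigger.
- **The 207 wording can be reconciled.** The Synopsis, End-of-Study Definition and Section 8.6.7 all express a minimum, so enrolling until 207 data sets are complete would satisfy every one. A reader might infer a flat contradiction; the documents support only an ambiguity. It still needs settling, because no section says which sense governs. The gap between 186 and 188 is itself only two patients.
- **A detailed SAP is promised in Section 8.** It could add interval reporting, but it cannot enlarge a stratum, and 8.5 makes its claim now.
- **The by-Clonidine evaluation is already labelled a sensitivity analysis.** That is true, but 8.5 extends its claim to all planned analyses without exception.

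**Conclusion.** The point holds as a matter of unsupported wording. Section 8.5 supports a five-term refit and nothing more. Even there, if 207 means included, the expected count falls marginally short of the plan's own 75, and reaching it is about an even chance.

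Three stronger readings are tempting and are not supported:

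- **That 207 is too small.** The documents set no precision target, so sufficiency can be neither confirmed nor refuted.
- **That each Clonidine stratum needs 75 events.** Section 8.3.2.3 evaluates an existing model and does not fit a new one.
- **That neither stratum can be informative alone.** Only the untreated stratum has a known upper bound. The treated share is given only as a majority; at an assumed 90% of 188 analysed (169 patients) the slope half-width at AUC 0.70 would be 0.47, against 0.44 pooled, so that stratum would be nearly the whole sample.

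The event probabilities rest on the plan's 40% rate and 10% loss. The AUC and slope widths rest also on the assumed AUC range, and the slope widths on the normal linear predictor. This should be corrected; it does not call the design into question.

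**What to change.** 1. **Section 8.5.** Limit the adequacy sentence to the refit and say that 75 events is expected, not assured. Give expected 95% half-widths for the event rate, pooled AUC and pooled calibration slope under stated assumptions, and note that the slope widths are approximate and optimistic in small strata.
2. **Synopsis, End-of-Study Definition, Sections 8.5 and 8.6.7.** Give 207 one meaning, included or complete, and restate the analysed number and expected events to match.
3. **Section 8.3.2.3.** Report both Clonidine strata with 95% confidence intervals, labelled descriptive. State that the untreated stratum cannot by itself confirm or refute the matrix. Make no such statement for the treated stratum while its size is unknown.

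The cost is a less favourable adequacy statement and some rewording. No extra enrolment is proposed. If the sponsor keeps the complete-data meaning already in the End-of-Study Definition, about 230 would be included, which at 40 a month takes 230 / 40 = 5.75 months, within the 6 to 7 months in the Synopsis.
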